8.2 Statistical Methods

This is a pre-post analytical design and the primary statistical method will be a paired t-test, examining changes from baseline to 6 months. We will use a paired t-test to statistically measure changes resulting from the GAE procedure. Frequencies, including pre-post change, will be reported as percents with 95% confidence intervals. Continuous data will be reported as means with 95% confidence intervals. $P \leq 0.05$ will be considered to indicate statistical significance. All analyses will be performed using SAS software and confidence intervals will be reported as appropriate, including estimates for the appropriate sample size for a larger future study (v9.2, SAS Institute Inc., Cary, NC).

Any deviations from the previously described statistical plan will be described and justified in a protocol amendment and/or in the final report submitted to the IDE application. The causes of all missing values will be documented with the study data.

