4.2 Anticipated Number of Research Subjects

Enrollment into the investigation will be defined as providing informed consent for study participation per IRB policies.

Twenty (20) subjects will be enrolled between both sites and all are anticipated to complete the study.

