4.6.2 Follow-up for Withdrawn Subjects

If a subject withdraws from the study, any recorded data will still be included in the analysis. Subjects will only be replaced if they withdrew prior to undergoing GAE.

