6.6 Visit 6 - 6 Month Follow-Up

Subjects will be seen in clinic or contacted by phone or by teleconference per the subject's preference 180 +/- 10 days following GAE. The WOMAC questionnaire and VAS pain score will be completed and subjects will be evaluated for possible adverse events. Subjects will also provide an update about the necessity/frequency of

pre-established conservative therapies. If an AE is suspected based on change in pain scores or functionality, an appropriate work-up will be performed which may include MRI.

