8.0 Statistical Plan

8.1 Sample Size Determination

Only one small study has examined the use of transcatheter arterial embolization for the treatment of knee pain secondary to OA (12). In that study, the baseline WOMAC total score (mean±SD) was 48.5±9.4. The primary outcome of this study is a 16% reduction in the baseline WOMAC total score. Using the baseline total score from that study, a sample size of 15 will have 80% power to detect a 16% difference (7.8 points) in means, assuming a standard deviation of 10 points. Conservatively, to protect against a potential lost-to-follow-up of 30%, 20 total subjects will be enrolled. This sample size also will ensure adequate power for the secondary outcome, a reduction in the VAS by 15% at 6 months follow-up.

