8.3 Subject Population(s) for Analysis

A patient will be considered an evaluable study subject evaluable for data analysis per the following criteria, a written informed consent was obtained, he/she meets the inclusion and exclusion criteria, and received the GAE study procedure. All subjects with 6 month follow-up data will be included for analysis even if some follow up data is incomplete. Every attempt will be made to ensure that there is as little missing data

as possible including reminder phone calls and follow-up phone calls if a subject misses a visit.

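### The 6-month estimate rests on completers only; a supportive mixed model using the 1- and 3-month scores would be a cheap safeguard

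*Combined protocol and SAP*

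**What the plan says.** - **Test.** In section 8.2, "the primary statistical method will be a paired t-test, examining changes from baseline to 6 months". The section also plans 95% confidence intervals for means and percents. On missing values it asks only that their causes be recorded.
- **Analysis set.** Section 8.3 makes a subject evaluable on consent, eligibility and having had the procedure ("and received the GAE study procedure"). It then adds: "All subjects with 6 month follow-up data will be included for analysis even if some follow up data is incomplete". It does not say what happens to an evaluable subject without a 6-month score.
- **Withdrawals.** Section 4.6.2: "If a subject withdraws from the study, any recorded data will still be included in the analysis". Also: "Subjects will only be replaced if they withdrew prior to undergoing GAE". A subject lost after treatment is therefore not replaced.
- **Expected loss.** Section 8.1 plans "to protect against a potential lost-to-follow-up of 30%, 20 total subjects will be enrolled", while section 4.2 says "all are anticipated to complete the study".
- **Data collected.** WOMAC and VAS are scheduled at baseline and at 1, 3 and 6 months (sections 6.1 and 6.4 to 6.6). Month 6 can be done remotely: "Subjects will be seen in clinic or contacted by phone or by teleconference" (section 6.6).
- **Use of the results.** Sections 2.0 and 8.2 both intend the data to inform the sample size of a future study.

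**The concern.** A paired t-test needs both scores, so a subject seen at months 1 and 3 but not at month 6 contributes nothing to it. Section 4.6.2 promises that such data will be used, and the descriptive means could carry them, but no named test or 6-month estimate does. No sensitivity analysis is planned.

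The size of the reported effect is at stake. If subjects who do poorly are more likely to leave, those who remain look better than the treated group as a whole. Such a link is plausible: section 5.4 allows no new or escalated therapy apart from short post-operative medication, and a subject whose pain returns may prefer to leave. The documents do not show that this will happen, and starting a therapy is not a removal criterion in section 4.6.1. A future study sized on an inflated change would be too small.

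**Working it through.** **1. The plan's own figure.** Inputs from section 8.1: baseline WOMAC 48.5, a 16% reduction, SD 10, 80% power. The difference is 0.16 × 48.5 = 7.76, stated as 7.8. Taking 10 as the SD of the paired change and a two-sided level of 0.05, exact noncentral-t power at n = 15 is 0.802, so the stated 15 reproduces. A 30% loss from 20 leaves 20 × 0.70 = 14 pairs, with power 0.770. Power is only slightly affected; the question here is which subjects the 14 are.

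**2. Mean change among completers.** Assumptions, not from the documents: 60% of subjects respond by a mean of 15 points at month 6 and 40% by 0, so the true mean is 0.6 × 15 = 9.0. Let a and b be the loss probabilities in responders and non-responders.

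Expected loss = 20 × (0.6a + 0.4b)

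Completer mean = 0.6(1−a) × 15 / [0.6(1−a) + 0.4(1−b)]

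| Loss a / b | Expected lost of 20 | Completer mean (truth 9.0) |
|---|---|---|
| 5% / 15% | 1.8 | 8.55 / 0.91 = 9.4 |
| 30% / 30% | 6.0 | 6.30 / 0.70 = 9.0 |
| 20% / 45% | 6.0 | 7.20 / 0.70 = 10.3 |
| 10% / 60% | 6.0 | 8.10 / 0.70 = 11.6 |

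**3. What the 1- and 3-month scores recover.** This was simulated with n = 20, within-group SD 8 and visit-noise correlation 0 or 0.5. Maximum likelihood for monotone missingness stood in for an unstructured mixed model. "Early" means non-responders never improve. "Late" means they improve by 15, 7.5 and 0 points at months 1, 3 and 6. All lost subjects are assumed seen at months 1 and 3.

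| Loss a / b | Completers | Model, early | Model, late |
|---|---|---|---|
| 5% / 15% | 9.4 | 9.1–9.2 | 9.3 |
| 30% / 30% | 9.0 | 9.0 | 9.0 |
| 20% / 45% | 10.3 | 9.2–9.5 | 9.9–10.1 |
| 10% / 60% | 11.6 | 9.5–10.3 | 10.8–11.3 |

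At 20%/45%, the 95% interval covers the truth 92% of the time for completers and 95–96% for the model. The model's root-mean-square error was similar to or lower than that of completers throughout.

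**4. Consequence for sizing.** Required n varies as 1/(change)². If the next study were sized directly on this change with the SD held fixed, using 10.29 in place of 9.0 gives (9.0/10.29)² = 0.77 of the n needed, about 23% too few.

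**5. Success rates, if reported.** Suppose 6 of 20 are lost and 11 of the 14 seen succeed (an assumed count). The completer rate is 11/14 = 79% (exact 95% CI 49–95%). The worst case over all treated is 11/20 = 55% and the best case 17/20 = 85%. With 1 lost and 15 of 19 succeeding, 79% compares with bounds of 15/20 = 75% and 16/20 = 80%.

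**The case against.** **Section 8.3 already implies an observed-case set.** This stands as the natural reading. The plan does have an inclusion rule, and section 4.6.2 can be squared with it through the descriptive summaries. What is missing is any 6-month estimate that uses the partial data and any check on the completer figure. Nor is the t-test the only inference, since confidence intervals are planned too.

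**Loss may be small.** This also stands. The 30% is offered as a conservative margin, all subjects are expected to finish, and remote visits and reminder calls are planned. With about 2 lost, the completer mean is 9.4 against 9.0.

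**A reader might infer that the pilot's result is biased or its significance test unsafe.** The documents do not support that. No link between loss and outcome is shown, and in the 20%/45% illustration both 10.3 and the true 9.0 exceed 7.76.

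**A reader might infer that a missing score should simply count as failure or as zero change.** Those rules can miss by more than the completer figure. At 20%/45% the true success rate (at least 7.76 points) is 56%; completers give 61% and missing-as-failure 43%. With loss unrelated to outcome, completers are correct at 56% and 9.0 points, against 39% and 6.3. Zero change can thus fall below 7.76 when the truth is above it. Such rules serve as bounds, not estimates.

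**A reader might take a per-subject success rate as a stated endpoint.** It is a plausible reading of sections 7.2 and 8.2, but section 8.1 powers a difference in means and no section fixes the format.

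**The model is weakest for the mechanism named.** This stands. If pain returns late, it leaves about 67–83% of the completer bias at 20%/45% (0.87 to 1.07 of 1.29 points).

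**Conclusion.** The concern holds in a limited form. Treated subjects lost before month 6 leave the 6-month estimate, even though the plan collects usable earlier scores from them and says recorded data will be included. If loss depends on poor response, the completer change is too favourable: 10.3 against 9.0 with about 6 of 20 lost at 20%/45%, and 11.6 under stronger dependence. If loss is about 2 of 20, or unrelated to outcome, the difference is 0.4 points or none. All these figures rest on an assumed responder mix, SD and loss pattern; they illustrate and do not estimate the bias in this trial. The matter is the reported effect size and its use in planning. Weight: minor to moderate, a cheap improvement.

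**What to change.** 1. Keep the paired t-test as primary.
2. In section 8.2, prespecify a supportive repeated-measures mixed model on baseline, 1-, 3- and 6-month WOMAC and VAS, in all eligible subjects who received GAE whether or not they have a 6-month score. Use unstructured covariance and Kenward-Roger degrees of freedom, and name a simpler structure as fallback, since four visits in at most 20 subjects may not support the full one.
3. Report its 6-month change beside the completer change, and consider both when sizing the next study.
4. State the limit: the model reduces bias but does not remove it, and helps least when pain returns late.
5. If per-subject 16% and 15% success rates are reported, give the completer rate with worst- and best-case bounds over all treated subjects, labelled as bounds.
6. Align sections 8.3 and 4.6.2 so that it is clear which analysis uses a withdrawn subject's data.

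The cost is a few sentences and one standard SAS model on data already collected, with no new visits or subjects. The downside is slightly more analysis work and possibly a less favourable reported effect.

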8.3 Subject Population(s) for Analysis

A patient will be considered an evaluable study subject evaluable for data analysis per the following criteria, a written informed consent was obtained, he/she meets the inclusion and exclusion criteria, and received the GAE study procedure. All subjects with 6 month follow-up data will be included for analysis even if some follow up data is incomplete. Every attempt will be made to ensure that there is as little missing data

as possible including reminder phone calls and follow-up phone calls if a subject misses a visit.

8.4 Interim Analysis

An interim analysis will not be conducted.

9.0 Risk Analysis

9.1 Anticipated Risks

Previous studies of lower extremity geniculate artery embolization for arthritis related pain have reported only one complication of moderate puncture site related hematoma (1/13), however this was a small population (12). A recent study of GAE for recurrent hemarthrosis completed by one of the co-PIs ([name]) included 2/13 subjects who developed transient cutaneous ischemia that resolved within three weeks without intervention (8). Additional risks that are anticipated but occur infrequently after any arterial intervention include infection, pain, pseudoaneurysm formation, arterial dissection and distal non-target embolization resulting in ischemia or necrosis. Detailed risk analysis is below:

	Risk or Side Effect	Source of Risk or Side Effect	Possible	Less Possible	Rare Event
Potential Risks Associated Study Enrollment & Study Procedures	Discomfort	Blood draw for lab test, ultrasound or MRI	X		
	Thrombophlebitis, bruising, bleeding, blood clot, Pre-syncope or Syncope (i.e. Fainting)	Blood draw for lab tests		X	
	Anxiety or Claustrophobia	MRI scan		X	
	Psychological Discomfort	Clinical Trial Enrollment			X
	Infection	Blood draw for lab tests			X
	Allergic Reaction	MRI contrast injection			X
	Gadolinium contrast adverse reaction (ie. Nephrogenic Systemic Fibrosis or severe skin reaction from contrast agent only reported in patients with kidney dysfunction)	MRI Contrast injection			X
	Confidentiality breach from Medical Records	Medical Record Keeping			X
	Groin/Anesthetic Injection/Neurologic Injury/Discomfort/Pain	Pressure during arterial access and after catheter removed at the leg/femoral artery site	X		
	Radiation Exposure Injury	GAE procedure			X
	Kidney Dysfunction	Contrast injected during procedure		X	

Risks of the GAE Procedure and Postoperative care	Joint Infection	GAE Procedure		X	
	Adverse or Allergic Reaction	Intravenous contrast agent or medications administered as part of procedure or follow-up care (ie. MRI contrast)		X	
	Tissue damage to Skin, Muscle, Skin or other structure in legs (Non-target Embolization)	GAE procedure			X
	Minor Bruising or Bleeding	GAE procedure			X
	Bleeding requiring Transfusion or surgery	GAE procedure			X
	Synovitis related symptoms including pain, stiffness or limited joint mobility	GAE procedure	X		
	Post Embolization Syndrome, including fever, malaise, headache, and myalgia (body aches)	GAE procedure		X	
	Internal bleeding, such as Gastrointestinal bleeding	Medications taken after the procedure (ie. Ibuprofen)			X
	Infection	Catheter site in the leg/groin			X
	Arterial injury/trauma, laceration, bruising/pseudoaneurysm	Procedure/ Closure device (clip) on the artery			X
	Pulmonary embolism (clot in lung), Thrombophlebitis (clot in artery or vein)	GAE procedure and immobility			X
	Myocardial Infarction (Heart attack)	GAE procedure including moderate sedation/sedative medication			X
	Stroke	GAE procedure including moderate sedation/sedative medication			X
	Disability	GAE procedure including moderate sedation/sedative medication			X
	Death	GAE procedure including moderate sedation/sedative medication			X

9.2 Risk Minimization

The GAE procedure will be performed by board-certified interventional radiologists who have expertise in endovascular techniques, particularly in selective catheterization and transcatheter embolization techniques. Analgesia during the procedures will be provided through the use of conscious sedation if required. The risks of conscious sedation will be minimized by continuous monitoring of heart rate, blood pressure, oxygen saturation, and

cardiac rhythm. The dose area product projected for the procedure is thought to be less than 30 gray/cm² which is about 2-4 years of background radiation and significantly less than that of a cardiac catheterization. Radiation exposure will be minimized to subjects under the principal of 'as low as reasonably achievable' (ALARA).

Sterile instruments with a sterile technique will be used to minimize infection risk at the arterial access site. Pre-operative antibiotic(s) will be administered to reduce risk of other infections, such as urinary tract. The arterial access site discomfort will be minimized by administration of local anesthesia into the overlying skin and adjacent tissues. Catheter access into the appropriate artery may be performed using ultrasound-guided arterial puncture to prevent inadvertent vessel puncture with subsequent bleeding. Real-time fluoroscopic monitoring of all catheter/wire manipulations will be used to prevent vascular injury.

Cone beam CT, which provides cross sectional anatomic detail prior to embolization, will be available to the operating interventional radiologist. This angiographic technique can mitigate the risk of non-target embolization. The intent of this technique, as well as meticulous angiographic technique will be used to minimize the risk of non-targeted embolization, that could lead to skin or soft tissue/muscle injury.

The subject will be monitored for the risk of an allergic response to iodinated contrast. To minimize the risk of renal dysfunction there will be use of non-ionic contrast agents, and appropriate pre-procedure hydration, when necessary. Subjects who report an allergic reaction to iodinated contrast will be pre-medicated as per routine allergy prophylaxis per standard of care.

9.3 Adverse Event Definitions

Adverse effect. Any untoward medical occurrence in a clinical study of an investigational device; regardless of the causal relationship of the problem with the device or, if applicable, other study treatment or diagnostic product(s).

Associated with the investigational device or, if applicable, other study treatment or diagnostic product(s). There is a reasonable possibility that the adverse effect may have been caused by the investigational device or, if applicable, the other study treatment or diagnostic product(s).

Disability. A substantial disruption of a person's ability to conduct normal life functions.

Life-threatening adverse effect. Any adverse effect that places the subject, in the view of the investigator-sponsor, at immediate risk of death from the effect as it occurred (i.e., does not include an adverse effect that, had it actually occurred in a more severe form, might have caused death).

Serious adverse effect. Any adverse effect that results in any of the following outcomes: death, a life-threatening adverse effect, inpatient hospitalization or prolongation of existing hospitalization, a persistent or significant disability/incapacity, or a congenital anomaly/birth defect.

- *Hospitalization* shall include any initial admission (even if less than 24 hours) to a healthcare facility as a result of a precipitating clinical adverse effect; to include transfer within the hospital to an intensive care unit. Hospitalization or prolongation of hospitalization in the absence of a precipitating, clinical adverse effect (e.g., for a preexisting condition not associated with a new adverse effect or with a worsening of the preexisting condition; admission for a protocol-specified procedure) is not, in itself, a serious adverse effect.

Unexpected adverse effect. Any adverse effect, the frequency, specificity or severity of which is not consistent with the risk information described in the clinical study protocol(s) or elsewhere in the current IDE application, as amended.

Unanticipated adverse device effect. Any serious adverse effect on health or safety or any life-threatening problem or death caused by, or associated with, a device, if that effect, problem, or death was not previously identified in nature, severity, or degree of incidence in the investigational plan or IDE application (including a supplementary plan or application), or any other unanticipated serious problem associated with a device that relates to the rights, safety, or welfare of subjects.

9.2 Recording of Adverse Events

Research subjects will be questioned about adverse effects in person or by telephone the day following the procedure. In addition they will be given a pager number to reach a physician 24 hours a day to report adverse effects and receive medical advice. The subjects will also be questioned about possible adverse effects at each follow-up visit.

All observed or volunteered adverse effects (serious or non-serious) and abnormal test findings, regardless of treatment group, if applicable, or suspected causal relationship to the investigational device or, if applicable, other study treatment or diagnostic product(s) will be recorded in the subjects' case histories. For all adverse effects, sufficient information will be pursued and/or obtained so as to permit 1) an adequate determination of the outcome of the effect (i.e., whether the effect should be classified as a *serious adverse effect*) and; 2) an assessment of the causal relationship between the adverse effect and the investigational device or, if applicable, the other study treatment or diagnostic product(s).

Adverse effects or abnormal test findings felt to be associated with the investigational device or, if applicable, other study treatment or diagnostic product(s) will be followed until the effect (or its sequelae) or the abnormal test finding resolves or stabilizes at a level acceptable to the investigator-sponsor.

An abnormal test finding will be classified as an *adverse effect* if one or more of the following criteria are met:

- The test finding is accompanied by clinical symptoms
- The test finding necessitates additional diagnostic evaluation(s) or medical/surgical intervention; including significant additional concomitant drug treatment or other therapy

- Note: simply repeating a test finding, in the absence of any of the other listed criteria, does not constitute an adverse effect.
- The test finding leads to a change in study protocol or discontinuation of subject participation in the clinical research study
- The test finding is considered an adverse effect by the Sponsor-Investigator.

9.3 Causality and severity assessment

The investigator-sponsor will promptly review documented adverse effects and abnormal test findings to determine 1) if the abnormal test finding should be classified as an adverse effect; 2) if there is a reasonable possibility that the adverse effect was caused by the investigational device or, if applicable, other study treatment or diagnostic product(s); and 3) if the adverse effect meets the criteria for a *serious adverse effect*.

If the investigator-sponsor's final determination of causality is "unknown and of questionable relationship to the investigational device or, if applicable, other study treatment or diagnostic product(s)", the adverse effect will be classified as *associated with the use of the investigational device or study treatment or diagnostic drug product(s)* for reporting purposes. If the investigator-sponsor's final determination of causality is "unknown but not related to the investigational device or, if applicable, other study treatment or diagnostic product(s)", this determination and the rationale for the determination will be documented in the respective subject's case history.

